## 9.3 EXPLORATORY OUTCOMES OF INTEREST

N/A

## 10 DATA QUALITY

## 10.1 DATA COLLECTION PROCEDURES AND DATA ELEMENTS

Data will be extracted from the implanted ICD or CRT-D device. Patient-reported outcomes (PROs) will be collected via the Pattern Health smartphone App. Patients will report study-related AEs through the App. Any reported AEs will be followed up with a phone call and screening in the EMR. At study conclusion, the EMR will also be screened for any unreported AEs.

### 10.1.1 PATIENT REPORTED DATA AND DEVICE DATA

Patient reported data collected via the Pattern Health Patient App include weight, questionnaire responses, blood pressure and blood sugar, review of current medications, recent hospitalization and the presence of symptoms (shortness of breath or chest pain).

Devices used in this study will be integrated with the Pattern Health App and the data collected will be passively uploaded to the Duke EMR.

Device data for this study include:

- Abbott Medical ICD or CRT-D implantable device: heart rate, daily physical activity, physical activity intensity, and heart failure severity

All AEs will be gathered electronically through the Pattern health smartphone application. The study coordinator will request addition information through the App on an individual basis. In the event that a subject fails to respond to requests for data through the App, a follow-up telephone call will be placed by a study coordinator. All AEs will be recorded in the eCRF.

### 10.1.2 DUKE EPIC EMR

The Duke EMR will be used to collect the results of recent testing (echocardiograms, ECGs) and will be used to ascertain if the patient has experienced any study related adverse events.

## 10.2 DATA COLLECTION AND MANAGEMENT

### 10.2.1 PATTERN HEALTH APP DATA

Data will be de-identified at the earliest opportunity, and PHI will be stored only for purposes of subject identification by the PI and study staff as necessary during the course of the study. The data collected by the Pattern Health Patient application will be stored on HIPAA compliant Pattern Health server.

Pattern Health research data will be transferred directly to the DCRI statistical team via Duke Box.

## 10.2.2 REDCAP

The Electronic Data Capture (EDC) used for this study is REDCap. Data will be entered electronically by site study staff into REDCap. The study site is expected to enroll all participants into REDCap and enter data within 72 business hours of enrollment or each subsequent study visit/procedure/contact.

Corrections to eCRFs should be performed using REDCap, which will track modifications in the audit history. The audit history contains the date, time, field name, and username of the individual who modified the study data.

REDCap is a secure, web-based application for building and managing online databases, hosted by the Duke Office of Clinical Research (DOCR). REDCap provides automated export procedures for seamless data downloads to Excel and common statistical packages (SPSS, SAS, Stata, R), as well as a built-in project calendar, a scheduling module, ad hoc reporting tools, and advanced features, such as branching logic, file uploading, and calculated fields.

All REDCap users are expected to be trained and to be able to perform project responsibilities within the REDCap before obtaining access to the live study.

### 10.3 MONITORING PLANS

Due to the short time between trial startup and completion along with the single center study design and relatively small number of enrolled subjects, no DSMB will be convened for the project

## 10.4 DATA QUALITY ASSURANCE

This study will be conducted under Good Clinical Practice (GCP) and all applicable regulatory requirements. To ensure compliance, the sponsor or designee may conduct a quality assurance audit.

Actions to ensure the accuracy and reliability of data include the selection of qualified investigator and appropriate study center; the review of protocol procedures with the investigator and study personnel prior to study start; the design of suitable source documents with appropriate instructions for use (where applicable); the internal audit of source data according to GCP and internal procedures to ensure their accuracy, completeness, and verifiability.

## 11 STATISTICAL ANALYSIS PLAN (SAP)

### 11.1 OVERALL STATISTICAL APPROACH AND ANALYSIS POPULATION

#### 11.1.1 HYPOTHESES

Hypothesis for Primary Endpoint 1 (P1): We hypothesize that the change in median of physical activity from baseline to 12 weeks as measured by Abbott ICD and CRT-D device will be larger (more physical activity) among patients randomized to remote CR versus usual management. Our null hypothesis is that there is no difference in the two groups.

Hypothesis for Secondary Endpoint 1 (S1): We hypothesize that the change in KCCQ HF symptom severity score mean from baseline to 12 weeks as measured by KCCQ questionnaire will be lower (less severity) among patients randomized to remote CR versus usual management. Our null hypothesis is that there is no difference in the two groups.

Hypothesis for Secondary Endpoint 3 (S3): We hypothesize that the change in PA measured by the Abbott ICD or CRT-D device between baseline and end of follow up and change in KCCQ HF symptoms severity scores during same time period will be negatively correlated. With greater increases in PA measurements being correlated with greater reduction in KCCQ HF severity scores.

#### 11.1.2 OVERALL STATISTICAL APPROACH

All tests will be tested in no particular sequence. There will be no interim analysis. As this is a hypothesis generating study, we will not employ a mechanism to address alpha spending (multiplicity) within the secondary endpoint family.

For P1 and S1-S2, we will be reporting 95% confidence intervals, mean at baseline, mean at terminal timepoint, Multilevel Model estimates over the timepoints of interest, and related p values.

For the S3, we will be reporting the strength of the correlation and related p values.

Additionally, alpha levels will be set at 0.05, and all tests will be two sided unless otherwise stated. All these statistics will be obtained via SAS 9.4 or higher. Please see Section 11.2 for how continuous and categorical variables will be reported. Values obtained from scheduled measurement time points will be included in data summaries tables and listings. We will utilize the Shapiro-Wilk or goodness of fit tests to assess normality.

#### 11.1.3 ANALYSIS POPULATION/DATASETS

Effectiveness will be assed in the Intent-To-Treat (ITT) population and in the Per-Protocol (PP) population. Both analysis populations will be examined for all objectives, however, the success of the trial will be based on the analysis of the ITT population.

**Intent-to-Treat (ITT) Population:** All participants who were randomized. Subjects will be analyzed according to the treatment group to which they were randomized, regardless of whether they received that intervention. This population will include participants who may have received the wrong intervention and have protocol violations.

**Safety Analysis (SA) Population:** All participants who had at least one session on the study app.

**As-Treated (AT) Population:** The treatment assignment of this population will be based on the actual treatment patients received, not the treatment the patients were randomized to receive. Deviations related to treatment compliance with randomized intervention: Participants not meeting the adherence requirement of completing at least 2/3 of expected app check in sessions will be considered a protocol deviation and excluded from the PP analysis population.

Any additional exclusion of any subject from a data presentation, other than those described above and in the section on handling of missing data, will be considered on a case-by-case basis, and will be described in the final study report.

## 11.2 BASELINE DESCRIPTIVE STATISTICAL ANALYSIS

For the baseline descriptive summaries, continuous variables will be summarized using number of observations (n), mean, standard deviation (SD), median, 25th and 75th percentiles, minimum, and maximum.

All categorical variables will be summarized using frequency counts and percentages. The calculation of percentages will be based on the number of patients with non-missing measurements for that time point in the corresponding category. P values for Wilcoxon rank sum test or Pearson chi-square test or Fisher's exact test will also be reported.

## 11.3 STUDY SUCCESS AND FAILURE CRITERIA

The success of the study will depend on finding a statistically significant difference in the change in mean from baseline to week 12 in:

Physical activity as measured by Abbott ICD and CRT-D devices for the ITT population.

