**Exclusion Criteria**

- Prior participation in CR within the last year
- Unwillingness to sign informed consent form
- Currently performing <40 or >240 minutes of device detected daily PA
- Lack of a smartphone or unwillingness to use an App or Garmin device
- Prior left ventricular assist device (LVAD) implantation or heart transplantation
- ICD tachyarrhythmia therapies programmed off
- Inherited arrhythmia condition with contraindication to exercise (eg Lamin A mutation or ARVC)
- No transmissions through Merlin.net in past 12 months

---

Endpoints:	
Aim 1: Compare the median Abbott ICD and CRT-D device measured daily PA obtained over the 1 month before randomization (baseline) and 12 weeks after randomization among patients randomized to remote CR versus usual management.
 
Aim 2: Compare baseline and 12 week Kansas City Cardiomyopathy Questionnaire (KCCQ) HF symptom severity scores among patients randomized to remote CR versus usual management.
 
Aim 3: (Safety) Report Adverse Events of heart failure hospitalization, fracture, myocardial infarction, serious adverse arrhythmia, and ICD therapy.
 
Aim 4: Measure the correlation between change in daily PA measured by the Abbott ICD or CRT-D device between baseline and end of follow up and change in KCCQ HF symptoms severity score measured between baseline and end of follow up.

Statistical Methods:	Multilevel Modeling (MLM), Wilcoxon rank-sum tests and Pearson's correlation will be used to compare outcomes across treatment assignment. The expected sample size will be 50 subjects.
Target Population:	We will enroll patients followed in the Duke Health System Abbott Medical Merlin remote monitoring dataset who have heart failure and prior implantation of an ICD or CRT-D device. Patients will be ≥18 years of age. No enrollment restrictions will be based on gender or race.
Description of Sites/Facilities:	This will be a single center study performed at Duke University Health System.

---

Description of Study Intervention:	The study intervention will be a patient directed exercise prescription based on device measured physical activity and provided by a smart phone application.
Study Duration:	11 months
Participant Data Duration:	12/30/2020 to 11/15/2021
Additional Data Captured:	N/A

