## 11.5 COMPUTATION OF DERIVED VARIABLES

Weekly averages:

1. Baseline mean: Average of all measurements in a month prior to randomization.
2. Week 4 mean: Average of all measurements in week 4.
3. Week 8 mean: Average of all measurements in week 8.
4. Week 12 mean: Average of all measurements in week 12.
5. Change from baseline to Week 12 mean: Difference of week 12 mean from baseline mean.
- 1.

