## 11.8 ENDPOINT ANALYSIS

### 11.8.1 PRIMARY ENDPOINT ANALYSIS

General statistical approach to primary endpoint: This endpoint will be analyzed in both the ITT and PP populations. Missing data will be handled as described in Section 11.12.

Analysis strategy for P1:

The outcome variable for this objective is the median Abbott ICD and CRT-D device measured daily PA obtained over the 1 week before randomization (baseline) and week 4, week 8, and week 12 after randomization. This endpoint represents a summary measure. The hypothesis test will evaluate whether the trajectory of the mean Abbott ICD and CRT-D device measured in the remote CR treatment group is different from the trajectory in the usual management group. The test will be a multilevel modeling (aka mixed models) on trajectories of the outcomes over the study period.

P1: Compare the trajectory of the median Abbott ICD and CRT-D device measured daily PA obtained over the 1 week before randomization (baseline) and week 4, week 8, and week 12 after randomization among patients randomized to remote CR versus usual management.

Reporting for P1: Descriptive summaries of the median physical activity at baseline and 4 weeks, 8 weeks, and 12 weeks after randomization will be presented by treatment group. The estimated differences in slopes of trajectories from CR and usual care treatment groups will be presented, along with the p-values by comparing the trajectories over study period. If differences are noted with regard to baseline covariates adjusted analyses will be performed for the primary endpoint.

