4.1.1 Analysis Population

Effectiveness will be assessed in the Intent-To-Treat (ITT) population and in the As-treated (AT) populations. Both analysis populations will be examined for all objectives, however, the success of the trial will be based on the analysis of the ITT population.

- Intent-to-Treat (ITT) Population: All participants who were randomized. Subjects will be analyzed according to the treatment group to which they were randomized, regardless of whether they received that intervention. This population will include participants who may have received the wrong intervention and have protocol violations.
- Safety Analysis (SA) Population: All participants who had at least one session on the study app.
- As-Treated (AT) Population: The treatment assignment of this population will be based on the actual treatment patients received, not the treatment the patients were randomized to receive.

Deviations related to treatment compliance with randomized intervention: Participants not meeting the adherence requirement of completing at least 2/3 of expected app check in sessions will be considered a protocol deviation and excluded from the AT analysis population.

Any additional exclusion of any subject from a data presentation, other than those described above and in the section on handling of missing data, will be considered on a case-by-case basis, and will be described in the final study report.

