6.3 Primary Endpoint Analyses

P1: Compare the trajectory of the median Abbott ICD and CRT-D device measured daily PA obtained over the 1 month before randomization (baseline) and week 4, week 8, and week 12 after randomization among patients randomized to remote CR versus usual management.

Analysis strategy for P1: The outcome variable for this objective is the median Abbott ICD and CRT-D device measured daily PA obtained over the 1 month before randomization (baseline) and week 4, week 8, and week 12 after randomization. This endpoint represents a summary measure. The hypothesis test will evaluate whether the trajectory of the mean Abbott ICD and CRT-D device measured in the remote CR treatment group is different from the trajectory in the usual management group. The test will be a multilevel modeling (aka mixed models) on trajectories of the outcomes over the study period. In the multilevel model, time (week of study), treatment group, and the interaction between treatment group and time will be handled as fixed effects. Time will be modeled as a continuous variable. The model will include random effects for subject-specific intercepts and slopes, with unstructured covariance for random intercepts and slopes.

Reporting for P1: Descriptive summaries of the median physical activity at baseline and 4 weeks, 8 weeks, and 12 weeks after randomization will be presented by treatment group. The estimated difference in slopes of trajectories from the CR and usual care treatment groups will be presented, along with the p-value for comparing the trajectories over the study period. If differences are noted with regard to baseline covariates adjusted analyses will be performed for the primary endpoint.

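### Success is defined as a change in mean activity to week 12, the only main P1 test is a slope difference, and no text says that its p-value decides

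*Protocol*

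**What the plan says.** **Success rule.** Protocol 11.3 ties success to "finding a statistically significant difference in the change in mean from baseline to week 12" in physical activity (PA) in the ITT population. SAP 4.1.1 agrees on the population: "the success of the trial will be based on the analysis of the ITT population". Protocol 11.5 derives a matching variable, "Change from baseline to Week 12 mean: Difference of week 12 mean from baseline mean", but no P1 test uses it.

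**P1 test.** Protocol 11.8.1: "The estimated differences in slopes of trajectories from CR and usual care treatment groups will be presented, along with the p-values". SAP 6.3: "The estimated difference in slopes of trajectories from the CR and usual care treatment groups will be presented, along with the p-value". Time is continuous there, and "The model will include random effects for subject-specific intercepts and slopes, with unstructured covariance for random intercepts and slopes". The SAP does not restate the success rule, and SAP 5.1 declares no departure from the protocol that affects the analysis.

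**Mean or median.** Protocol 11.1.1 frames the hypothesis as "the change in median of physical activity from baseline to 12 weeks". Protocol 11.8.1 and SAP 6.3 take median daily PA as the outcome, then describe the test as one on the trajectory of the mean. Protocol 3.1, 9.1, 11.1.2 and 11.5 speak of means or averages. The missing-data text (Protocol 11.12, SAP 6.6) refers to weekly averages but fills gaps with a median.

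**Power.** Protocol 11.4 and SAP 4.2 give 81.1% for aim 1 with 28 patients. The synopsis plans 50 patients, and SAP 4.1 says 13.

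**Baseline-adjusted check.** SAP 6.7 and Protocol 11.12 add baseline PA as a covariate to the same model, test the treatment variable, and also report the adjusted slope difference.

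**Baseline window for PA.** One week in Protocol 7.4, 9.1 and 11.8.1; one month in the synopsis, Protocol 8.4.1 and 11.5, and SAP 3.1, 4.1.2 and 6.3.

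**The concern.** A binary success rule needs one named test. Here the rule names a two-point change and the analysis delivers a four-point slope. Whoever reports the trial must supply the link, after seeing the data and without blinding. If the effect arrives early and levels off, or arrives late, the slope and the change estimate different numbers of minutes, and the reader cannot tell which one the sponsor committed to.

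Three related matters affect the same claim. The stated power belongs to a sample that SAP 4.1 contradicts. The treatment-term p-value in the baseline-adjusted check could be mistaken for a test of the effect. The starting point of the primary outcome has two definitions.

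**Working it through.** **Inputs.** From Protocol 11.4 and SAP 4.2: SD 19, within-subject correlation 0.7, four time points, 15 minutes per day (at week 12, per SAP 4.2), 28 patients at 1:1, alpha 0.05. Two-sided testing is in Protocol 11.1.2. Assumed: equal correlation between all times, no dropout, baseline at week 0, no random-slope variance.

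**1. The plan's own figure.** For weeks 0, 4, 8 and 12, the weights for 12 x slope are -0.9, -0.3, 0.3 and 0.9, with sum of squares 1.8.
- Variance per patient: 361 x 0.3 x 1.8 = 194.94.
- SE at 14 v 14: sqrt(194.94 x 2/14) = 5.28.
- Power: Phi(15/5.28 - 1.96) = 81.1%, as stated (78.1% with a t reference on 26 df).

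The stated power is therefore that of the slope test.

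**2. The quantity in Protocol 11.3.** Variance of the change: 2 x 361 x 0.3 = 216.6. SE 5.56. Power 76.9% (73.8% with t).

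**3. When the two agree.** Let d be the between-group difference at each week. With complete data,

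12 x slope difference = 0.9(d12 - d0) + 0.3(d8 - d4).

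This equals d12 - d0 when d8 - d4 = (d12 - d0)/3. Linearity is sufficient but not necessary. Illustrative profiles (assumed):

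| d at weeks 0/4/8/12 | 12 x slope | Change |
|---|---|---|
| 0/5/10/15 | 15 | 15 |
| 0/2/7/15 (not linear) | 15 | 15 |
| 0/15/15/15 | 13.5 | 15 |
| 0/0/15/15 | 18 | 15 |
| 0/15/10/5 | 3 | 5 |

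**4. Other sample sizes.** Slope test at 25 v 25: 96.7% (96.1% with t). At 13 patients, taken as 6 v 7: SE = sqrt(194.94 x (1/6 + 1/7)) = 7.77, power about 49% (42% with t). The change test at 13 has about 45% (39%).

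**5. Random slopes.** SAP 6.3 fits them, but the power allows them no variance and the documents give none. Adding a slope SD s adds 144s^2 to the variance of 12 x slope. For s = 0.25, 0.5 and 1.0 minutes/day per week, power at 28 falls to 79.4%, 74.3% and 57.8%. These figures also raise the outcome SD above the plan's 19 (at week 12, to sqrt(361 + 144) = 22.5 for s = 1.0). They show direction, not the power under the plan's inputs.

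**6. If a change-score t-test were run as well.** In 40,000 simulated trials at 28 patients with a linear effect, it and the slope test fell on different sides of 0.05 in about 9%. The rate was 9.7% for 0/15/15/15 and between 7% and 8% for 0/15/10/5, but 16% to 17% for 0/0/15/15. Under no effect, taking whichever was significant rejected in about 6.5%.

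**7. The treatment term in the baseline-adjusted model.** With treatment x time in the model, this term is the group difference at the week coded zero. For a linear effect of 15/12 = 1.25 minutes per week, its expected value is 0 with zero at baseline, 7.5 with zero at week 6, and 15 with zero at week 12. The documents do not state the coding.

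The adjusted slope adds little. With baseline kept among the responses and complete data, it equalled the main slope in refits with random intercepts only. With baseline removed, it covers weeks 4 to 12: variance 144 x 361 x 0.3/32 = 487.4, SE 8.34, power 43.6%.

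A baseline-adjusted week-12 difference has variance 361 x (1 - 0.49) = 184.1 and power 83.3% at 28 (about 51% at 13).

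**The case against.** The strongest defence is that the plan has one main P1 test. The slope reading is the one that reproduces the 81.1%, SAP 4.2 places the 15 minutes at week 12, and in the SAP's linear model 12 x slope is the modelled week-12 change with the same p-value. On that reading 11.3 is loose wording. This is a fair reading and is the basis of the fix, but neither document states it.

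Several stronger readings are tempting and are not supported:
- **Two competing tests, so inflated type I error.** The SAP plans no change-score test for P1. The synopsis lists "Multilevel Modeling (MLM), Wilcoxon rank-sum tests" without an endpoint, and the only body section that uses Wilcoxon is Protocol 11.2, for baseline summaries. The 6.5% applies only if a test is added.
- **Non-linearity as the main cause of conflicting p-values.** Two separately run tests would disagree in about 9% of trials even under a linear effect, from sampling noise. Of the profiles simulated, only a late step raised this clearly.
- **Mean contradicts median throughout.** A patient-level median analysed through group means is coherent, and the mean in 11.3 may be the group mean. The real conflict is over the patient-level summary, chiefly Protocol 9.1 and 11.5 against 11.8.1 and SAP 6.3.
- **50 contradicts 28.** Aim 1 needs 28, aim 2 needs 50, and enrolling 50 covers both. Only the 13 conflicts with the stated power.

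It is also fair to say that the baseline-adjusted model does not decide success, that its adjusted slope is reported too, and that the study is declared hypothesis-generating.

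**Conclusion.** The point holds in a limited form. Protocol 11.3 names a change to week 12, the planned test is a slope difference, and no text joins them. Under the plan's inputs the gap in power is about 4 points at 28 patients (81.1% against 76.9%), and the estimates differ by 1.5 to 3 minutes in the non-linear profiles tabulated. At 13 patients the stated power does not describe the trial: about 49%, or 42% with t, assuming a 6 v 7 split. The documents do not explain the 13. The treatment-term test is uninformative about the effect if baseline is week 0, and ambiguous otherwise.

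All power figures assume equal correlations, complete data and no random-slope variance. What is at stake is how a pilot declares and reports success, and what it passes on to the pivotal trial foreseen in Protocol 9.1. No confirmatory claim is at risk.

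**What to change.** (a) In Protocol 11.3 and SAP 6.3, state that the ITT slope-difference p-value (two-sided 0.05) decides success, and report the estimate also as 12 x slope. Choose one patient-level weekly summary, median or mean of daily PA. Keep the word mean where it refers to the group trajectory. Align Protocol 3.1, 9.1, 11.1.1, 11.1.2, 11.5, 11.8.1 and 11.12, and SAP 3.1, 6.3 and 6.6.

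(b) In Protocol 11.4 and SAP 4.2, restate the power of that test at the number in SAP 4.1, or correct the 13. Say that the figure assumes no random-slope variance.

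(c) In SAP 6.7 and Protocol 11.12, delete the test of the treatment main effect. Report instead a baseline-adjusted week-12 contrast with its CI, with baseline PA as a covariate and not as a response, labelled as a sensitivity check. Add its table to SAP section 7, which lists tables only for the imputed and transformed sensitivity analyses.

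(d) Use one baseline PA window, reconciling Protocol 7.4, 9.1 and 11.8.1 with the synopsis, Protocol 8.4.1 and 11.5, and SAP 3.1, 4.1.2 and 6.3.

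Cost: wording in these sections and one extra table, with no new data or software. Keeping the median and the one-month window needs the fewest edits, because the synopsis, Protocol 11.1.1 and SAP 3.1 could then stand on those two points.
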